6.4. Non-study Drug Medications

6.4.1. Concomitant Medications

Prior medications are those taken before the first dose of study drug. Concomitant medications are those administered on or after the first dose of study drug, or those administered before the first dose that are ongoing when study treatment begins. Prior and concomitant medications will be coded using World Health Organization drug enhanced dictionary (March 2017 version or higher) and summarized using the FAS.

Separate tables will be generated to summarize prior CAD medical treatment, concomitant CAD medical treatment, and protocol prohibited CAD treatment.

6.4.2. Other Therapies and Procedures

All other therapies received during the study (whether for CAD or other condition) will be summarized for the FAS and listed.

6.5. Study Drug

Study drug exposure and compliance will be summarized using the Safety Analysis Set. Subject-level information on dosing with study drug will also be provided in a data listing.

6.5.1. Exposure

Study drug exposure, measured by the duration of study treatment, number of administrations, and total actual BIVV009 dose, will be summarized for the Safety Analysis Set.

The duration of the study treatment (in weeks) in Part A is defined as:

- $(\text{date of Week 26 visit} - \text{date of first dose} + 1)/7$, if a subject enrolls into Part B;
- $(\text{date of last dose} - \text{date of first dose} + 15)/7$, if a subject discontinues study treatment early in Part A or does not enroll into Part B.

The actual dose administered at each visit is calculated as:

$(\text{Total volume administered} / \text{Total volume prepared}) * \text{assigned dose}$.

The total BIVV009 dose is the summation of all actual dose administered in Part A.

6.5.2. Compliance

Study drug compliance for a subject is measured by the percent of number of doses received out of the number of protocol specified doses. For example, for a subject who completes Part A treatment, the number of protocol specified doses is 14. The compliance of the subject will be the number of doses received divided by 14 expressed in percentage. For a subject who discontinues early in Part A, the number of protocol specified doses is the number of scheduled doses prior to the date of discontinuation. The proportion of subjects whose compliance is less than 80%, 80% – < 100%, and $\geq 100\%$ will also be summarized. In addition, the number of subjects and number of doses administered out of study windows and number of partial infusion doses will also be summarized.

7. EFFICACY ANALYSIS

7.1. General Efficacy Principles

Unless specified otherwise, all analyses described will be performed for Part A.

7.1.1. Multiplicity

The study hypothesis described in [Section 3.2](#) will be tested at a 1-sided significance level of 0.025. No other formal hypothesis will be tested, as secondary endpoints will be estimated along with associated 95% CIs.

7.2. Primary Endpoint

The primary endpoint, defined in [Section 2.2.1](#), is a composite endpoint of the following components:

1. Free of post-baseline transfusion within the range of Week 5 and Week 26 visit dates;
2. Hgb at treatment assessment timepoint ≥ 12 g/dL, or the change from baseline at treatment assessment ≥ 2 g/dL,
3. Receive no protocol prohibited medications defined in [Section 5.1.1](#).

Components 1 and 3 will be determined by the corresponding questions in eCRF at all visits (from Week 5 through Week 26) in Part A.

To be evaluable for each of the components, a subject must be observed through at least Week 23 visit. Discontinuation of study treatment prior to Week 23 visit will result in an unknown status for Components 1 and 3. Missing Hgb value at all visits of Week 23, 25, and 26 will result in an unknown status for Component 2.

In the event of unknown status in any of the components, a subject may be a responder, non-responder, or missing for the response status. A subject is considered responder, if the subject meets all of the three components; a subject is considered a non-responder, if the subject is known to not meet any of the three components; otherwise, a subject is considered missing in response status.

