A patient will be considered a responder in Part A if he or she did not receive a blood transfusion from Week 5 through Week 26 (EOT) and did not receive treatment for CAgD beyond what is permitted per protocol. Additionally, the patient's Hgb level must meet either of the following criteria:

- Hgb level is ≥ 12 g/dL at the treatment assessment endpoint (defined as mean value from Weeks 23, 25, and 26), *or*
- Hgb increased ≥ 2 g/dL from baseline (defined as the last Hgb value before administration of the first dose of study drug) at treatment assessment endpoint

Note: Any patient withdrawing from the study after Week 5 and prior to the Week 23 visit will be considered a non-responder.

A list of excluded concomitant medications, as well as allowed concomitant medications with restrictions, is provided in [Section 6.2.6](#). Beyond the permitted concomitant medications, study drug, and transfusions, patients may receive no other therapies for the treatment of CAgD while enrolled in this study; patients requiring other treatment for their CAgD in Part A will be withdrawn from the study and counted as non-responders. These patients will not be eligible to participate in Part B.

Part B

Following completion of dosing in the 6-month treatment period, patients will continue to receive BIVV009 dosing during Part B, the long-term safety and durability of response extension phase. Part B will run for 2 years following last patient out (LPO) under Part A. Patients requiring treatment with permitted concomitant medications and/or transfusions will not be discontinued from the study. Patients in Part B will be transfused per the Transfusion Criteria in [Table 1](#). Patients who receive a transfusion during Part B will not be withdrawn from the study.

Patients will be dosed with BIVV009 every 2 weeks, as in Part A. Should patients deviate from their scheduled dosing, a repeat loading dose may be required. On-site visits will be completed ~ every 3 months (at a minimum) for collection of PK, PD and ADA samples during the 1st year of treatment in Part B, then every 6 months and for additional safety and efficacy measures.

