5.2.2. Categorical Variables

Categorical variables will be summarized by counts and percentages. All percentages will be rounded to one decimal place. The percentage will be suppressed when the count is zero. Unless specified otherwise, the denominator for all percentages will be the number of subjects with non-missing data for a given summarization. This number (n) will be included with categorical summaries unless the same variable is also being summarized with descriptive statistics, in which case 'n' will already be provided.

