7.2.1. Primary Analysis

The primary analysis of the primary endpoint involves the composite estimand ([Section 5.1.3](#)), for which **any missing response (above) will be considered a non-responder**. The proportion of subjects who respond according to the estimand ([Table 3](#)) will be estimated along with a 95% exact Clopper-Pearson CI.

To reject the null hypothesis of the response rate $\leq 30\%$, the lower bound of the 95% CI must be greater than 30%.

In addition, the proportion of subjects who meet each of the response criteria will be summarized.

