For either estimand, the mean change from baseline in LDH at treatment assessment timepoint, along with its 95% CI, will be estimated by the MMRM model ([Section 5.1.4.1](#)).

Additional sensitivity analyses for hypothetical estimand, similar to those specified for bilirubin, will be performed for the change from baseline in LDH at treatment assessment timepoint.

Additional descriptive analyses will be performed for LDH isoforms.

7.3.4. Number of Transfusions and Number of Units after the First 5 Weeks of Study Drug Administration

The number of transfusions after Week 5 through Week 26 visits will be summarized for the FAS, where the observed data will be used for subjects who discontinue study treatment early in Part A. The number of units transfused during the same period of time will be summarized for subjects who receive at least 1 transfusion.

The transfusions occurring during the first 5 weeks will be listed.

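### SAP 7.2 sets Components 1 and 3 to unknown after any stop before Week 23, with no exception for a failure already recorded, so the component table can drop known failures

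*SAP*

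**What the plan says.** The primary endpoint in SAP (Part A) 7.2 has three components: no transfusion between the Week 5 and Week 26 visits (1), the hemoglobin criterion (2), and no prohibited medication (3).

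- **Evaluability (SAP 7.2):** "To be evaluable for each of the components, a subject must be observed through at least Week 23 visit".
- **Early stop (SAP 7.2):** "Discontinuation of study treatment prior to Week 23 visit will result in an unknown status for Components 1 and 3". Neither sentence excepts an event already on record.
- **Response status (SAP 7.2, next paragraph):** "a subject is considered a non-responder, if the subject is known to not meet any of the three components". Anyone who is neither a responder nor a known non-responder is missing.
- **Primary analysis (SAP 7.2.1):** "any missing response (above) will be considered a non-responder".
- **Component summary (SAP 7.2.1):** "the proportion of subjects who meet each of the response criteria will be summarized", with no denominator given.
- **Default denominator (SAP 5.2.2), unless specified otherwise:** "the denominator for all percentages will be the number of subjects with non-missing data for a given summarization".
- **Other treatment for the disease (Protocol 4.1):** "patients requiring other treatment for their CAgD in Part A will be withdrawn from the study and counted as non-responders". The same section says that transfused patients are not withdrawn.

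**The concern.** Components 1 and 3 can be failed only once, and the failure cannot be undone. A patient transfused at Week 10 who stops at Week 12 has failed Component 1 whatever would have followed. Unknown status is right for an early stopper with no event. It is wrong for one whose event is recorded.

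Read literally, 7.2 codes both patients alike, and the default denominator then removes both from the component table. The loss is selective. SAP 5.1.4 itself expects prohibited treatment to be used mostly because of lack of response or breakthrough, and Protocol 4.1 withdraws patients who require other treatment for the disease. Before Week 23, the failing event would therefore normally lead to the stop that hides it.

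At stake is the description of how patients failed and of the transfusion-free proportion, which bears directly on the primary objective. The same Week 10 transfusion would be counted in SAP 7.3.4, "where the observed data will be used for subjects who discontinue study treatment early in Part A", while the component table called that patient unknown. The 7.2 paragraphs also leave two programmers free to code the same patient differently.

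**Working it through.** **1. The plan's own figure.** Inputs: 20 patients, null rate 30%, assumed true rate 66%, success if the exact 95% Clopper-Pearson lower limit exceeds 30% (SAP 3.3 and 7.2.1; Protocol 7.10 gives 11/20 as the smallest success).

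- Lower limit for 10/20: 27.2%; for 11/20: 31.5%. So 11 is the minimum, as stated.
- P(X ≥ 11) for X ~ Bin(20, 0.66): 89.7%, against the stated 90%.
- P(X ≥ 11) for X ~ Bin(20, 0.30): 0.0171, below the one-sided 0.025.

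**2. Effect on the primary result.** A patient who stops before Week 23 is either a known non-responder or missing, and missing counts as non-response. Table 3 in SAP 7.2.2 also requires remaining in study through Week 23. The responder count is the same under either coding. For example, an assumed 13/20 gives 65% (95% CI 40.8% to 84.6%) both ways.

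**3. Component 3.** The documents give no event counts, so the counts are assumptions shown over a range. Let *k* patients receive a prohibited drug and be withdrawn before Week 23, with no other failures or early stops.

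- Literal rule, default denominator: (20 − k)/(20 − k).
- Recorded event kept as a failure: (20 − k)/20.

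| k | Literal | Event kept |
|---|---|---|
| 1 | 19/19 = 100% | 19/20 = 95% |
| 2 | 18/18 = 100% | 18/20 = 90% |
| 3 | 17/17 = 100% | 17/20 = 85% |

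With 2 further early stops and no recorded event in those two, the literal figure is still 100% (17/17, 16/16, 15/15). Keeping the recorded events gives 17/18 = 94.4%, 16/18 = 88.9% and 15/18 = 83.3%.

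**4. Component 1.** Let 4 transfused patients stay and *m* further patients be transfused from Week 5 and then stop before Week 23, with no other early stops.

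- Literal: (16 − m)/(20 − m).
- Event kept: (16 − m)/20.

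| m | Literal | Event kept | Difference |
|---|---|---|---|
| 1 | 15/19 = 78.9% | 15/20 = 75% | 3.9 points |
| 2 | 14/18 = 77.8% | 14/20 = 70% | 7.8 points |
| 3 | 13/17 = 76.5% | 13/20 = 65% | 11.5 points |

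**5. How much of Component 3 is hidden.** If prohibited use were spread evenly over Weeks 5 to 26 with prompt withdrawal (an assumption), the share falling before Week 23 would be (23 − 5)/(26 − 5) = 18/21 = 86%. The other 3/21 = 14% would still show.

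**The case against.** The best reply is that the SAP may not mean what the sentence literally says. The next paragraph deals with unknown status and still provides for a subject known to fail a component, and 7.2 takes Components 1 and 3 from the eCRF questions at every visit from Week 5. Both suggest that recorded failures were meant to count. This stands as evidence of intent, but does not settle the coding. The known-failure rule governs response status and takes component status as its input, which the preceding paragraph has just set to unknown. SAP 5.1.4 points the other way, since a missing component there makes the endpoint missing.

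Second, 7.2.1 sits within an analysis on the full analysis set, and SAP 4.1 places efficacy analyses on that set. With that denominator the percentage meeting each component is not inflated. This also stands: the inflation depends on the 5.2.2 default applying. The wrong label would remain.

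Third, the information appears elsewhere: prohibited treatment has its own table (SAP 6.4.1), and transfusions are covered in 7.3.4 and in time to first transfusion (7.4.1.3). That limits the harm but does not correct the component table.

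A reader might infer that Component 3 can almost never show a failure. The documents do not support that. Use in Weeks 23 to 26 still shows, Protocol 5.3 says only that patients may be withdrawn for non-permitted medication, and the de-facto estimand in SAP 5.1.3 provides for values after such use. For Component 1 the problem needs both a transfusion from Week 5 and a separate stop before Week 23, so most transfusion failures should stay visible.

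**Conclusion.** The concern holds as a minor wording defect. SAP 7.2 has no exception for a recorded failure and fits poorly with the known-failure rule that follows it. Read literally and with the 5.2.2 denominator, the component table omits known failures. Each such patient among 20 is worth about 4 to 5 percentage points in the illustrations above. Those sizes rest on assumed event counts and on the default denominator being used.

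A reader might go further and conclude that the primary result is biased, or that the split into responder, non-responder and missing is plainly wrong. Neither follows. The responder rate, its interval and the test against 30% are the same under both codings. The split is unclear rather than demonstrably wrong, because the known-failure sentence can be read to rescue it. The completer estimand leaves out early stoppers by its own definition and is not part of this point.

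**What to change.** Replace the early-stop sentence in SAP 7.2 with: *Discontinuation before the Week 23 visit gives unknown status for Component 1 or 3 only if no qualifying transfusion (from Week 5) or prohibited medication was recorded before discontinuation; once one is recorded, the component is not met.* Make the evaluability sentence before it subject to the same exception.

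In 7.2.1, state that each component is reported over the full analysis set as met, not met or unknown. Apply this also to the second component table listed in SAP section 12, which uses the lower limit of normal for hemoglobin.

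The cost is a small edit to 7.2 and a table footnote. No new data are needed and the primary test does not change. The component rates may come out slightly less favourable.

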7.2.1. Primary Analysis

The primary analysis of the primary endpoint involves the composite estimand ([Section 5.1.3](#)), for which **any missing response (above) will be considered a non-responder**. The proportion of subjects who respond according to the estimand ([Table 3](#)) will be estimated along with a 95% exact Clopper-Pearson CI.

To reject the null hypothesis of the response rate $\leq 30\%$, the lower bound of the 95% CI must be greater than 30%.

In addition, the proportion of subjects who meet each of the response criteria will be summarized.

7.2.2. Sensitivity Analyses

Sensitivity analyses will be carried out based on the completer estimand and the per-protocol estimand (defined in [Table 3](#)). The proportion of subjects with treatment response will be summarized along with the 95% exact Clopper-Pearson CI.

Table 3: Estimands for Primary Endpoint

	Composite Estimand	Completer Estimand	Per-protocol Estimand
Population	FAS	A subset of FAS with those who complete treatment at least through Week 23 and have at least 1 evaluable Hgb from Week 23, 25, and 26	A subset of FAS with those who are free of important protocol deviations defined in Section 6.3
Response Variable	Responder if 
 Free of post-baseline transfusion within the range of Week 5 and Week 26 visit dates, and Hgb at treatment assessment timepoint ≥ 12 g/dL, or the change from baseline at treatment assessment ≥ 2 g/dL, and Receive no protocol prohibited medications defined in Section 5.1.1 within the range of Week 5 and Week 26 visit dates, and Remain in study through at least Week 23, and At least 1 evaluable Hgb from Weeks 23, 25, and 26 	Responder if 
 Free of post-baseline transfusion within the range of Week 5 and Week 26 visit dates, and Hgb at treatment assessment timepoint ≥ 12 g/dL, or the change from baseline at treatment assessment ≥ 2 g/dL, and Receive no protocol prohibited medications defined in Section 5.1.1 within the range of Week 5 and Week 26 visit dates 	Responder if 
 Free of post-baseline transfusion within the range of Week 5 and Week 26 visit dates, and Hgb at treatment assessment timepoint ≥ 12 g/dL, or the change from baseline at treatment assessment ≥ 2 g/dL
Treatment effect	Proportion of subjects who achieve the composite response variable (defined above)	Proportion of subjects who achieve the treatment response	Proportion of subjects who achieve the treatment response

In the case when there are at least 2 subjects who discontinue study participation prior to Week 5, a supportive analysis, similar to the primary analysis, will be performed by excluding those subjects who discontinue prior to Week 5.

In the case of normal ranges (LLN) varying across local labs, a sensitivity analysis will be performed for the primary endpoint by qualifying normalization of Hgb using \geq LLN, instead of ≥ 12 g/dL.

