7.10 SAMPLE SIZE CONSIDERATIONS

Approximately 20 patients with primary CAgD who have a recent history of transfusion will be enrolled.

If the true responder rate is estimated to be 66% and a minimum of 30% is required for success, then with 20 patients, there is 90% probability that the lower limit of the 95% CI will be at least 30%. The minimal observed rate for a successful efficacy claim is $11/20 = 55\%$.

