5.1.4. Handling of Missing Data

Best efforts will be utilized to minimize missing values. If a subject discontinues study treatment early, the subject will be asked to complete study assessments at EOT/safety follow up visit.

For the primary endpoint, which is a composite endpoint of avoidance of transfusion and improvement of Hgb at the treatment assessment timepoint (i.e., Weeks 23, 25, and 26), missing either component results in a missing value for the endpoint. The improvement of Hgb at the treatment assessment timepoint is missing only if no Hgb value is available for all 3 visits (Weeks 23, 25, and 26). Since pre-treatment Hgb is a key requirement to enroll in the study, it is reasonable to assume that all enrolled subjects have at least 1 Hgb prior to the study treatment, which constitutes the baseline Hgb value (see [Section 5.1.1](#)).

For the primary analysis of the primary endpoint, the composite estimand is utilized. Hence, a missing value will be considered a non-response. Other sensitivity analyses specified in [Section 7.2.2](#) will be performed to evaluate the impact of missing values, when appropriate. However, other responder-type endpoints will be analyzed using observed data only.

For the analysis of continuous variables (e.g., secondary endpoints), summary statistics will be computed based on observed data. To analyze lab parameter (e.g., Hgb, bilirubin, LDH) changes attributable to the study treatment (hypothetical estimand), values post any transfusion (after Week 5) or protocol prohibited CAD treatment (defined in [Section 5.1.1](#), after Week 5) will be

censored. The mean change from baseline will be estimated using Mixed Model for Repeated Measures (MMRM) along with its 95% CIs. Multiple Imputation will also be used to estimate the mean change from baseline at treatment assessment timepoint and its associated 95% CI. All these analyses assume missing at random (MAR).

Although the assumption of MAR cannot be verified, the mechanism of missing data due to transfusion or prohibited medication use described below supports such an assumption.

- The protocol (Table 1) specifies the transfusion criteria, which is comprised of the Hgb level.

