6.3. Protocol Deviations

All protocol deviations will be recorded throughout the study. Major and minor protocol deviations/violations are to be pre-specified prior to database lock. All major protocol deviations will be summarized for the FAS. All deviations, both major and minor, will be provided in a data listing.

Important protocol deviations (within Part A study treatment period) impacting efficacy assessment are defined as any of the following:

- Not meeting eligibility inclusion criteria #3,
- Missing at least 2 consecutive doses or 3 intermittent doses,
- Received protocol prohibited CAD treatment ([Section 5.1.1](#)),
- Free of transfusion after Week 5 but missing study assessments at all three visits of Weeks 23, 25, and 26.

Important protocol deviations will be summarized. Subjects who have had any of the important protocol deviations will be excluded from the PP population.

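### The completer analysis of the primary endpoint drops recorded failures along with missing outcomes, and the per-protocol set drops prohibited-treatment failures, so neither isolates the effect of missing data

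*SAP*

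**What the plan says.** The primary analysis (Part A SAP 7.2.1 and Table 3, composite estimand) keeps every treated patient and counts any missing response as non-response. Response needs three things: no transfusion between the Week 5 and Week 26 visits, sufficient haemoglobin at Weeks 23 to 26, and no prohibited medication in the same period.

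Two supportive analyses are then set out in SAP 7.2.2: "Sensitivity analyses will be carried out based on the completer estimand and the per-protocol estimand". Section 5.1.4 gives the purpose of the 7.2.2 analyses; they "will be performed to evaluate the impact of missing values, when appropriate". Protocol 7.3.2 makes a similar commitment.

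- **Completer set (Table 3):** "A subset of FAS with those who complete treatment at least through Week 23", and with at least one evaluable haemoglobin from Weeks 23, 25 and 26. All three response components are kept.
- **Per-protocol set (Table 3, SAP 6.3):** patients without any of four important deviations. These are inclusion criterion 3 not met; two consecutive or three intermittent missed doses; "Received protocol prohibited CAD treatment"; and transfusion-free after Week 5 but with all three late assessments missing. Component 3 is left out of its response variable.

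On what counts as failure, Protocol 4.1 says "patients requiring other treatment for their CAgD in Part A will be withdrawn from the study and counted as non-responders". SAP 7.2 says "a subject is considered a non-responder, if the subject is known to not meet any of the three components". The same SAP section also gives components 1 and 3 an unknown status if treatment stops before Week 23.

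**The concern.** A sensitivity analysis for missing data should hold observed outcomes fixed and vary only the unobserved ones. Here some patients with an observed failure are taken out of the denominator. SAP 5.1.4 itself expects that prohibited treatment would mostly follow lack of response or haematologic breakthrough, so excluding patients for it depends on outcome.

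At stake is how the supportive results are read. If the completer or per-protocol rate agrees with the primary rate or exceeds it, a reader will take that as robustness, although part of the agreement may come from having set failures aside. In a trial of about 20 patients, one or two such removals move the interval noticeably.

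**Working it through.** **Inputs from the documents.** Sample size: "Approximately 20 patients with primary CAgD who have a recent history of transfusion will be enrolled" (Protocol 7.10). The null rate is 30%, the assumed true rate 66%, the stated power 90%, and the stated minimum for success 11/20 (Protocol 7.10). The hypothesis "will be tested at a 1-sided significance level of 0.025" (SAP 7.1.1). Success requires an exact Clopper-Pearson 95% lower limit above 30% (SAP 7.2.1). Neither document gives an expected number of exclusions, so the counts below are assumptions.

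**Design figure.** For X ~ Binomial(20, p):
- P(X ≥ 11 | p = 0.66) = 0.897, against the stated 90%.
- P(X ≥ 11 | p = 0.30) = 0.017, below 0.025.
- The lower limit is the 2.5% quantile of Beta(x, n − x + 1). For 11/20 it is 31.5% (clears 30%); for 10/20 it is 27.2% (does not).

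The plan's 90% and 11/20 are reproduced.

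**Completer analysis.** Let R be the responders, K the recorded failures who leave before Week 23, and U the patients whose outcome is truly unknown.
- Primary rate: R/20.
- Completer rate: R/(20 − K − U). Everyone removed is already a non-responder in the primary analysis, so R does not change and the rate cannot fall.
- Rate that isolates missing data: R/(20 − U).

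With R = 10, where the primary result is 10/20 = 50.0% (lower limit 27.2%):

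| Assumed K, U | Completer as planned | Only unknowns removed |
|---|---|---|
| K = 1, U = 0 | 10/19 = 52.6% (28.9%) | 10/20 = 50.0% (27.2%) |
| K = 2, U = 0 | 10/18 = 55.6% (30.8%) | 10/20 = 50.0% (27.2%) |
| K = 1, U = 1 | 10/18 = 55.6% (30.8%) | 10/19 = 52.6% (28.9%) |

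In the second row no outcome is missing at all, yet the completer result crosses 30%. In the third row the crossing depends on the one recorded failure.

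**Per-protocol analysis.** Remove a responders and b non-responders from 11/20 (lower limit 31.5%). The rate is (11 − a)/(20 − a − b).
- a = 0, b = 2: 11/18 = 61.1% (35.7%).
- a = 1, b = 1: 10/18 = 55.6% (30.8%).
- a = 1, b = 0: 10/19 = 52.6% (28.9%), now below 30%.

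Missed doses and inclusion criterion 3 do not depend on outcome and can contribute to a. Prohibited treatment in Weeks 5 to 26 can contribute only to b. The direction overall is therefore open; the outcome-dependent exclusion pushes it upwards.

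**The case against.** Several points on the other side stand.

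- **Direction.** A reader might infer that both supportive analyses can only hold or raise the rate. That is true of the completer analysis but not of the per-protocol analysis, as 11/20 to 10/19 shows. The prohibited-treatment deviation also covers the whole Part A treatment period, whereas Table 3 counts use only from Week 5, so even that rule could remove a composite responder.
- **Missing data.** A reader might infer that missing data are not examined at all. The completer analysis is a complete-case contrast to a primary analysis that already takes the worst case. Any other handling of truly missing outcomes can only hold or raise the rate, so upward movement alone is no flaw.
- **Transfused patients.** Protocol 4.1 does not withdraw patients for transfusion. Those who continue stay in the completer set as failures. The fourth deviation in SAP 6.3 applies only to transfusion-free patients, so it does not drop transfused patients from the per-protocol set.
- **Component 3.** Its absence from the per-protocol variable is redundant while prohibited-treatment patients are excluded. It matters only once they are put back.
- **Definitions.** Protocol Table 2 refers to any cold agglutinin disease treatment beyond what is permitted; SAP 5.1.1 uses a shorter list. The two events overlap but are not identical.
- **Unknown status.** SAP 7.2 can be read as making early leavers unknown even after a recorded failure, and Protocol Section 7 gives the SAP precedence. This makes the rule ambiguous; it does not justify treating an observed event as missing.
- **Other analyses.** SAP 7.2.2 has two further conditional analyses. One excludes patients who discontinue before Week 5, which can also only hold or raise the rate; the other changes the haemoglobin threshold. Neither isolates missing outcomes.
- **Role.** Only the primary hypothesis is formally tested, Protocol 7.3.1 calls the per-protocol results supportive, and the per-protocol exclusions are listed with reasons. This limits the harm.

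None of this answers the core point: no specified analysis keeps recorded failures as failures while varying only the unknown outcomes.

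**Conclusion.** The point holds for the supportive analyses. The completer set pools recorded failures who leave before Week 23 with truly missing outcomes, so it can only hold or raise the rate and does not separate the two causes. The per-protocol set additionally removes patients who failed through prohibited treatment in Weeks 5 to 26, while its other exclusions can act in either direction.

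The primary analysis is not affected: on either reading of SAP 7.2 these patients are non-responders there. The documents therefore do not support an inference that the primary claim or its error rate is compromised.

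The size depends on how many recorded failures leave early, which the documents do not predict. With 10 responders among 20 and no missing outcomes, one removal leaves the lower limit below 30% (28.9%) and two take it above (30.8%). If no such patient occurs, the completer analysis needs no correction in practice. The change is worth making, but it concerns supporting evidence only.

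**What to change.** 1. **Table 3, completer set.** Define it as patients treated through Week 23 with an evaluable haemoglobin, plus every patient with a recorded failure before leaving (transfusion from Week 5, or cold agglutinin disease treatment beyond what is permitted), counted as non-responders. Only unknown outcomes are then excluded.
2. **SAP 7.2.** State that a transfusion or prohibited medication recorded from Week 5 remains a known failure after discontinuation, and that the unknown-status sentence does not override it. Reconcile the SAP's list of prohibited medications with the wording of Protocol Table 2, so that the failure event has one definition.
3. **SAP 6.3 and Table 3, per-protocol.** Do not exclude patients for prohibited treatment in Weeks 5 to 26, and restore component 3 to the response variable. Limit the fourth deviation to patients with no recorded failure; otherwise a transfusion-free patient withdrawn for prohibited treatment would still be dropped. State that doses scheduled after withdrawal do not count as missed, which matches the compliance denominator in SAP 6.5.2.

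The cost is SAP wording and one derivation flag before the Part A lock. If the lock has passed, the revised versions should be reported as additional analyses and labelled as such. The downside is that the supportive rates may be slightly less favourable.
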